In terms of diagnosis, UC can be confirmed through endoscopic and histological studies, whereas CD has no definitive diagnostic, and it is usually conducted based on history, physical examination and findings from endoscopic, radiological, laboratory and histological studies.

In terms of epidemiology, some of the CD and UC highest-incidence areas of the world are northern European countries, the United Kingdom and North America. Although the incidence and prevalence of UC and CD are beginning to stabilize in these high-incidence areas, they continue to rise in low-incidence regions (i.e: southern Europe and Asia). It is estimated that 1.4 million and 2.2 million people in the United States and Europe, respectively, suffer from IBD. Spanish incidence of IBD seems to have increased in the last years, and is also variable across regions; UC incidence is estimated at 0.6-8 patients per 100,000 inhabitants per year, whereas there seems to be 0.4-5.5 CD patients per 100,000

inhabitants per year. Spanish IBD prevalence, albeit very difficult to establish, is estimated at 87-110 cases per 100,000 inhabitants per year.

The onset of IBD typically occurs in the late adolescence and beginning of adult stages of life and patients tend to progress to relapsing and chronic disease conditions. IBD is known to exert a negative impact in patient's life both in terms of Health Related Quality of Life (HRQoL) and productivity, overall representing a major burden for society and health services.

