## 6. Methodology

### 6.1. Study design

In order to meet the objectives of the present study, a retrospective, non-interventional, multicentre observational study including 25 gastroenterology sites from all around Spain has been designed. Participating investigators will be gastroenterologists and will include consecutive patients diagnosed with UC or CD that started treatment with biologics between June 2011 and June 2013, after giving written informed consent. The study will consist of one only visit in which investigators will collect patients' sociodemographic (age, gender, race, level of education, smoking habits alcohol intake) and clinical (concomitant diseases, date of diagnosis, previous treatment, current treatment, disease activity when starting treatment with biologics and at the study visit, current situation in terms of treatment with biologics) data from medical charts or directly from patients (in case of discrepancy, the information coming from medical charts will be preferable). Time since patients started biological treatment until study visit or until lack of treatment response or until treatment change will constitute the reference period for the study. In order to fulfill current legislations regarding non-interventional studies, investigators will commit to follow usual clinical practice.

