### 6.4. Study procedure

#### 6.4.1. Study visits

The study will consist of only one visit in which investigators will inform patients about the study objective and methodology and the possibility to take part of it. All data will be collected during the study visit or retrospectively from patients' clinical chart after giving written informed consent. More detail on data collection is given on sections 6.4.3, 6.4.4 and 6.4.5.

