#### 6.4.4. Study variables

The following **sociodemographic variables** will be collected from patients' medical records or directly from patients during the study visit, straight after their inclusion in the study:

- Age
- Gender
- Race (caucasian, asiatic, latin, black, other)
- Level of education (uneducated, primary education, secondary education, university education)
- Working status (student, self-employed, employed by other, retired, housework, unemployed, temporarily unable to work, permanently unable to work, other)
- Smoking habits (non-smoker, ex-smoker, smoker, number of cigarettes per day)
- Alcohol intake (units per week).

The following **clinical variables** will be collected from patients' medical records (when available) or directly from patients during the study visit, straight after their inclusion in the study:

- Date of diagnosis (UD or CD).
- Disease activity at the beginning of the reference period and at the study visit through collection of the following variables:
  - For UC patients:
    - Partial Mayo Score (PMS) (9 point scale that excludes the endoscopic appearance of the mucosa)
    - General disease activity:
      - Mild: up to four bloody stools daily and no systemic toxicity
      - Moderate: four to six bloody stools daily and minimal toxicity
      - Severe: more than six bloody stools daily and signs of toxicity, such as fever, tachycardia, anaemia, raised erythrocyte sedimentation rate.
      - Fulminant: More than ten bloody stools daily, continuous bleeding, anaemia requiring blood transfusion, abdominal tenderness and colonic dilatation on plain abdominal radiographs.
    - Disease anatomic extent: proctitis, left-sided colitis or pancolitis.
    - Endoscopy findings:

- Normal or inactive disease
- Mild disease (erythema, decreased vascular pattern, mild friability)
- Moderate disease (marked erythema, lack of vascular pattern, friability erosions)
- Severe disease (spontaneous bleeding, ulceration).
- For CD patients:
  - Harvey-Bradshaw Index (HBI) (a simplified version of CDAI)
  - General disease activity:
    - Mild to moderate: ambulatory patients able to tolerate oral alimentation without manifestations of dehydration, toxicity, abdominal tenderness, painful mass, obstruction or >10% weight loss.

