- Urogenital manifestations of IBDComorbidities in UC and CD patients (defined as the coexistence of another medical condition alongside IBD, and does not imply causation) at the time of diagnosis and at the study visit, will be listed according to chosen according to the Charlson index:

Comorbidity Component	Score
Myocardial Infarction	1
Congestive Heart Failure	1
Peripheral Vascular Disease	1
Cerebrovascular Disease	1
Dementia	1
Chronic Obstructive Pulmonary Disease	1
Connective Tissue Disease	1
Peptic Ulcer Disease	1
Diabetes Mellitus	1 (mild), 2 (moderate- severe)
Moderate-Severe      Chronic      Kidney Disease	2
Hemiplegic	2
Leukemia	2
Malignant Lymphoma	2
Solid Tumor	2 (tumor), 6 (if metastasis)
Liver Disease	1 (mild), 3 (moderate-severe)
Acquired immunodeficiency syndrome (AIDS)	6

- Biological treatment/s for UC or CD followed during the reference period:
  - Starting date
  - Posology
  - Intensification of biological treatment: date and type of intensification
  - Continuing with the treatment
  - Date and reason for discontinuation, if applicable
  - New biological treatment prescribed after discontinuation, starting date, posology, continuing with the treatment, date and reason for discontinuation.
- Concomitant treatment with corticosteroids (e.g. prednisone, hydrocortisone, betamethasone, methylprednisolone, etc,) or immunosuppressives (e.g. Ciclosporin, Methotrexate, etc) during induction phase
  - Starting date, number of cycles

Other treatments followed before the reference period to be chosen from the following list:

- Aminosalicylates (e.g. mesalazine, Sulfasalazine, 5-ASA, etc), oral, enema, suppository.
- Corticosteroids (e.g. prednisone, hydrocortisone, betamethasone, methylprednisolone, etc), oral, enema, suppository.
- Thiopurines (e.g. azathioprine, mercaptopurine, etc).
- Immunosuppressives (e.g. Ciclosporin, Methotrexate, etc).
- Anti-diarrheal drugs.
- Pain medications.
- Antidepressants.
- Antibiotics.
- Use of alternative medicine (e.g. acupuncture, relaxation therapy, Qigong, herbal therapy, etc).
- Other (specify)

- Other treatments followed during the reference period to be chosen from the following list:
  - Aminosalicylates (e.g. mesalazine, Sulfasalazine, 5-ASA, etc), oral, enema, suppository.
  - Corticosteroids (e.g. prednisone, hydrocortisone, betamethasone, methylprednisolone, etc), oral, enema, suppository. Number of cycles
  - Thiopurines (e.g. azathioprine, mercaptopurine, etc).

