5.3. Disease characteristics

The analysis of continuous variables included the following variables:

- Time from diagnostic of disease (UC or CD) (time in months from the date of diagnostic until the date of informed consent).
- Charlson index.

The analysis of categorical variables included the following variables:

- Disease location (L1=terminal ileum; L2= colon; L3=ileum and colon; L4=upper gastrointestinal track; E1=proctitis; E2=left colitis; E3=extensive colitis).
- Disease behavior (only for CD patients) (B1=inflammatory; B2=stenosis; B3= fistulizing; B1p; B2p; B3p (p=perineal)).
- Extraintestinal manifestations:
 - Arthropathy and arthritis (yes/no).
 - Metabolic bone disease (yes/no).
 - Eye disease (yes/no).
 - Oral, aural and nasal disease (yes/no).

- Skin disease (yes/no).
- Hepato-pancreato-biliary disease (yes/no).
- Neurological disease (yes/no).
- Cardiovascular manifestations of IBD (yes/no).
- Pulmonary manifestations of IBD (yes/no).

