7.2. Primary efficacy endpoint

- **Primary endpoint:** Evaluate the impact of the co-morbidities profile in IBD patients on treatment response to biological therapy.

The analysis that will be performed to answer the objective will be the following:

In order to determine the level of correlation between the co-morbidities profile and treatment response, adjusting for sociodemographic and clinical profile of patients, two logistic regression models will be conducted. The dependent variable of the models will be the **lack of response during the induction phase and the loss of response during the maintenance phase**. In both models independent variables will include all comorbidities, as well as sociodemographic and clinical variables as covariates.

- The following potential variables will be considered for the analysis:
 - Crohn's Disease or Ulcerative Colitis.
 - Myocardial Infarction (yes/no).
 - Congestive Heart Failure (yes/no).
 - Peripheral Vascular Disease (yes/no).
 - Cerebrovascular Disease (yes/no).
 - Dementia (yes/no).
 - Chronic Obstructive Pulmonary Disease (yes/no).
 - Connective Tissue Disease (yes/no).
 - Peptic Ulcer Disease (yes/no).
 - Mild Chronic Hepatopathy (yes/no).
 - Diabetes Mellitus (yes/no).
 - Hemiplegic (yes/no).
 - Moderate-Severe Chronic Kidney Disease (yes/no).
 - Diabetes with lesions in target organs (yes/no).
 - Solid Tumor (yes/no).
 - Leukemia (yes/no).
 - Lymphoma (yes/no).

- Moderate-Severe Chronic Hepatopathy (yes/no).
 - Solid tumor with metastases (yes/no)
 - Acquired immunodeficiency syndrome (AIDS) (yes/no).
 - Gender.
 - Race (caucasian, asiatic, latin, black, other).
 - Level of education (uneducated, primary education, secondary education, university education).
 - Working status (student, self-employed, employed by other, retired, housework, unemployed, temporarily unable to work, permanently unable to work, other).
 - Smoking habits (non-smoker, ex-smoker and smoker).
 - Alcohol abuse (yes/no).
 - Time from diagnostic of disease.
 - Disease location.
 - Discontinuation the biological treatment (yes/no)
- Each one of the variables will be compared between the subjects with primary non-response vs primary response and primary response maintenance vs loss of response and those variables whose p-value is lower than 0.1 are considered potential variables for performing a logistic regression analysis.

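### Working status, smoking and alcohol have no reference date and may be taken at the study visit, years after the week-10 outcome, yet they are candidate predictors in both primary models

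*SAP*

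**What the plan says.** SAP 7.2 plans two logistic models, one for lack of response in the induction phase and one for loss of response in the maintenance phase. The same candidate list serves both. It includes "Working status (student, self-employed, employed by other, retired, housework, unemployed, temporarily unable to work, permanently unable to work, other"), smoking habits in three classes and alcohol abuse as yes/no. Each candidate is compared between response groups, those with p<0.1 go forward, and stepwise selection follows.

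Protocol 6.4.4 says that the sociodemographic variables "will be collected from patients' medical records or directly from patients during the study visit, straight after their inclusion in the study". No date is attached to the value. Other items in the same section do have time points. Disease activity is "Disease activity at the beginning of the reference period and at the study visit", comorbidities are taken "at the time of diagnosis and at the study visit, will be listed", and treatments are split into before, induction and during the reference period.

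There is one visit, and "All data will be collected during the study visit or retrospectively from patients' clinical chart after giving written informed consent" (Protocol 6.4.1). Protocol 6.1 adds that "in case of discrepancy, the information coming from medical charts will be preferable". SAP 5.1 places these variables under a demographic and baseline heading but does not define baseline for them. Where the SAP does date a candidate predictor, time from diagnosis, it uses the visit: "time in months from the date of diagnostic until the date of informed consent" (SAP 5.3).

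The outcomes are dated from the start of treatment, which falls between June 2011 and June 2013. Primary non-response is judged at 10 weeks, and loss of response at 6 months or later with no upper limit (SAP 7.1).

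**The concern.** A patient's answer about current employment, given at the visit, complies with the plan. For the induction model that answer comes after the outcome. The protocol's own background recognises the pathway: "IBD is known to exert a negative impact in patient's life both in terms of Health Related Quality of Life (HRQoL) and productivity". A patient whose first biologic failed may be unable to work at the visit for that reason, and a patient with a serious comorbidity may be unable to work because of it. Inability to work would then be a common effect of the exposure and the outcome, and conditioning on it biases the comorbidity odds ratio, which is the primary quantity of interest. Smoking and alcohol may also have changed since treatment began, although the case is weaker for them.

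There is a second consequence even without that bias. Protocol section 4 aims at a scale that predicts response. A variable that follows the outcome cannot serve that aim, yet its odds ratio would be reported among the predictors.

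**Working it through.** **Planned sample size.** Protocol 7.1 gives 10 events per variable × 10 variables ÷ 0.50 = 200 per disease. This reproduces and is not in dispute.

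**Time gap.** The protocol gives no visit date, but its reference list cites a 2016 consensus paper, so visits before 2016 are implausible. Assuming visits in 2016:
- shortest gap: start 30 June 2013, visit 1 January 2016; (915 − 70) ÷ 365.25 = 2.3 years after week 10;
- longest gap: start 1 June 2011, visit 31 December 2016; (2040 − 70) ÷ 365.25 = 5.4 years.

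Later visits widen the gap.

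**Bias in the comorbidity odds ratio.** Assumptions, not document figures: one comorbidity with 20% prevalence and no true effect on response. Non-response is 30% (the upper figure in Protocol section 4), with 50% (Protocol 7.1) as a check. Let u00, u10, u01 and u11 be the probability of being unable to work at the visit with neither, comorbidity only, non-response only, and both. Within a working-status stratum the true odds ratio is multiplied by:
- able to work: (1−u11)(1−u00) ÷ [(1−u10)(1−u01)]
- unable to work: u11·u00 ÷ (u10·u01)

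For 5/20/20/35% these are 0.65×0.95 ÷ (0.80×0.80) = 0.965 and 0.35×0.05 ÷ (0.20×0.20) = 0.44. The adjusted model combines the two strata. Logistic regression on the expected table, with response as outcome and comorbidity and working status as predictors, gives:

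| u00/u10/u01/u11 (%) | Comorbidity OR, 30% non-response | Comorbidity OR, 50% | Spurious OR for unable to work (30%) |
|---|---|---|---|
| 5/15/25/40 | 0.79 | 0.81 | 5.4 |
| 5/20/20/35 | 0.80 | 0.83 | 3.6 |
| 3/10/10/17 | 0.92 | 0.93 | 2.8 |
| 5/15/10/20 | 0.94 | 0.94 | 1.8 |
| 5/10/8/15 | 0.97 | 0.97 | 1.6 |

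**Passing the p<0.1 screen.** Working status has nine categories, so the chi-squared test has 8 df. Suppose a share p0 is unable to work at start in both groups and a further fraction q of the remaining non-responders becomes so; then p1 = p0 + (1−p0)q. With r the non-response rate and p̄ = r·p1 + (1−r)·p0, the noncentrality is λ = N·r(1−r)(p1−p0)² ÷ [p̄(1−p̄)].

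Example: N=400, r=0.30, p0=0.07, q=0.10. Then p1 = 0.163, p̄ = 0.098 and λ = 8.2. The 8-df critical value at 0.10 is 13.36, and the pass probability is 0.62. As a yes/no variable (1 df) it would be 0.89. With p0=0.07 and 8 df:
- q of 10% to 15%: about 0.62 to 0.91 at N=400, and 0.36 to 0.62 at N=200;
- q of 5%: about 0.17 to 0.25 across both sizes;
- a true null: 0.10.

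**The case against.** The strongest reply is that the documents do not say these items are recorded as of the visit. In a one-visit retrospective study every item is entered at or after the visit, including baseline disease activity, and the date of entry is not the date of the value. Charts are an allowed source and are preferred on discrepancy, so a chart value may well date from treatment start. This stands: a reader might infer that the three variables are always visit-time values, and the text does not support that. It does not remove the point. The chart preference applies only when sources disagree, no chart date is specified, and the latest entry complies. The data could be an inseparable mix of values from before and after the outcome.

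Three further replies also stand in part.
- A reader might infer that the order is reversed in both models. It is not shown for loss of response, which has no upper time limit and may be judged close to the visit.
- A reader might infer that working status will generally pass the screen. With 8 df this is likely only for moderate or strong links.
- The bias is modest beside sampling error. With 400 patients, 20% comorbidity and 30% non-response, the standard error of the log odds ratio is √(1/24 + 1/96 + 1/56 + 1/224) = 0.273, so the 95% range around 1 is about 0.59 to 1.71. If the screen also applies to each comorbidity, a truly null one reaches the model only about 10% of the time, which limits false protective findings. It does not protect a real effect from being understated.

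Finally, other entries share the timing problem: discontinuation of the biologic, disease duration counted to consent, and comorbidity dated at diagnosis and visit. Correcting these three covariates does not settle those.

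**Conclusion.** The point holds as a missing reference date with a real consequence. The plan permits values that post-date the week-10 outcome by years to enter the induction model; for the loss-of-response model the order is undefined. In every scenario tabulated, adjustment moved a true comorbidity odds ratio of 1.00 downwards, to between 0.79 and 0.97, and gave inability to work a spurious odds ratio of 1.6 to 5.4. These sizes rest wholly on assumed probabilities and on a single pooled comorbidity, whereas SAP 7.2 lists 19 separate ones; the milder half of the range is small. The gap of at least about 2.3 years is inferred.

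A reader might conclude that working status should be struck from the models altogether. The documents do not support that: Protocol 7.4 calls for adjustment for sociodemographic profile, and working status at treatment start would be a legitimate covariate. The problem is its date.

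**What to change.** In Protocol 6.4.4 and the eCRF, record working status, smoking and alcohol as of the start of the first biologic, from the chart. In SAP 7.2, admit only values dated at or before that start as candidates in the primary models, and keep visit-time values for description. If working status at start proves largely unavailable, leave it out of the models, which also removes 8 degrees of freedom from a candidate list already well above the protocol's 10-variable ceiling.

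The cost is a few lines of protocol and SAP text and an eCRF instruction; the 200 per disease is unchanged. The downside is that some patients will have no start-dated value. Report how many for each variable, and handle them by a missing-data method stated in advance, because an 'unknown' category alone can introduce bias of its own.

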In the recent years, the aim of IBD treatment has evolved from symptomatic control to deep remission, which is defined as the absence of symptoms, markers of inflammatory activity, and endoscopic lesions, and is associated with fewer admissions to hospital, surgeries and better HRQoL. Main current treatment modalities for UC and CD include 5-aminosalicylates, corticosteroids, immunomodulators (including thiopurines, methotrexate, tacrolimus, cyclosporine, and biological therapies), and surgery. Conventional treatment with corticosteroids and immunomodulators has not been able to reduce the complications of the disease or modify its course. Over the last decade, biologic treatments, such as infliximab, adalimumab, certolizumab pegol, golimumab and vedolizumab has been used in patients with moderate to severe CD, and in those with acute severe UC who failed to respond to corticosteroids.

At present, early introduction of immunomodulators and biologic agents in patients with more serious disease is probably the most widely accepted management strategy. Treatment of IBD with anti-TNF $\alpha$  since IBD diagnosis, albeit capable of inducing and maintaining mucosal healing and reducing surgery and hospitalization rates, may imply overtreatment of patients with milder forms of disease, thus emphasizing the need for accurate prognostic markers to guide patient selection. It is worth mentioning that although anti-TNF $\alpha$  therapy is thought to be an effective approach for IBD, up to 30% of patients do not respond to induction therapy (primary non-response) and a significant proportion loses response over time (secondary non-response). Very often patients profile in randomized controlled trials is quite restrictive and not representative of patients routinely treated under usual clinical conditions, especially, in terms of presence co-morbidities, concomitant treatments and previous use of biologics.

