#### 6.4.5. Main outcome

Non responders will be those patients not achieving a reduction in HBI of at least 2 points from baseline for CD, and a decrease in the PMS of at least 2 points for UC.. In the cases where these indexes are not available, clinical response will be evaluated according to physician criteria at short term (10 weeks after starting the anti-TNF) and at long term (at least 6 months after starting the anti-TNF). Primary non-responders (PNR) were defined as patients with no clinical response at short term. Loss of response (LOR) was defined as loss of the effect of the drug along the follow up in a patient with initial response.

Reasons to stop the drug will be classified as follows: PNR, LOR, side effects (SE), remission and other.

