## 7. Statistical Analysis

### 7.1. Sample size calculation

Response to treatment with biologics is estimated at 50%, meaning that half of included patients are expected to be non-responders. Considering a minimal sample of 10 patients that present the event of interest per independent variable included in the logistic regression model and a maximum of 10 independent variables per model, a minimum estimated sample of 200 UC patients and 200 CD patients is required.

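### SAP 7.2 lets treatment discontinuation, which follows treatment start and is partly caused by the outcome, into both primary models, and leaves age off the candidate list

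*SAP*

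**What the plan says.** SAP 7.2 sets out two logistic models, one for lack of response in induction and one for loss of response in maintenance, "adjusting for sociodemographic and clinical profile of patients". One candidate list serves both. It holds disease type, 19 comorbidities and nine other items, the last being "Discontinuation the biological treatment (yes/no". Each candidate is compared between outcome groups, and "those variables whose p-value is lower than 0.1 are considered potential variables for performing a logistic regression analysis". Automatic stepwise selection follows, with no covariate forced in. The reported results are odds ratios with confidence intervals and p-values, plus sensitivity and specificity.

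On stopping, Protocol 6.4.5 states: "Reasons to stop the drug will be classified as follows: PNR, LOR, side effects (SE), remission and other". SAP 6.1 gives the same reasons and adds partial response. Protocol 6.4.4 collects "Date and reason for discontinuation, if applicable" for biologics used in the reference period. Protocol 6.1 runs that period from the start of the biologic "until study visit or until lack of treatment response or until treatment change will constitute the reference period". SAP 7.1 judges primary non-response at 10 weeks and loss of response at 6 months or later.

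Age is collected (Protocol 6.1 and 6.4.4) and summarised (SAP 5.2), but it is not in the SAP 7.2 list.

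**The concern.** A stop recorded for primary non-response or loss of response happens because response was judged to have failed. For those patients the covariate is a consequence of the dependent variable. The yes/no item also pools stops for remission, which follow from good response, and stops for side effects. With no time window, a stop long after week 10 can serve as a predictor of the week-10 result.

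The screen gives no protection: the more closely stopping reflects the outcome, the more surely it is selected. Once it is in the model, the comorbidity odds ratio is conditional on a later event, and sensitivity and specificity partly describe a result of non-response. Protocol section 4 wants a scale that predicts response, and stopping is unknown when treatment starts.

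Age is a separate omission. If it is related to both comorbidity and response, a comorbidity odds ratio that is not adjusted for it carries part of the age effect, in either direction.

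**Working it through.** **1. The plan's own figures.** Protocol 7.1: 10 events per variable × 10 variables ÷ 0.50 non-response = 200 per disease, which reproduces the stated sample. Candidates in SAP 7.2: 1 + 19 + 9 = 29.

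**2. Inputs.** From the documents: "up to 30% of patients do not respond to induction therapy (primary non-response" (Protocol section 4; 20% and 30% were run) and "Response to treatment with biologics is estimated at 50%, meaning that half of included patients are expected to be non-responders" (Protocol 7.1). The documents give no stopping rates, comorbidity prevalence, age mix or classification cut-off, so those below are assumptions.

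**3. Effect on the comorbidity odds ratio.** Write NR for non-responder, R for responder and C for comorbid. Among patients who stopped,

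OR = true OR × [P(stop | NR, C) ÷ P(stop | R, C)] ÷ [P(stop | NR, not C) ÷ P(stop | R, not C)].

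Among those who did not stop, the same formula holds with 1 − P.

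- No separate route (comorbid and other responders both stop in 30%, all non-responders in 90%): the multiplier is 1, so the OR stays at 2.00, or at 1.00 under the null.
- Comorbid responders stop in 45%: 2 × (0.90/0.45) ÷ (0.90/0.30) = 1.33 among stoppers, and 2 × (0.10/0.55) ÷ (0.10/0.70) = 2.55 among the rest. The main-effects logistic fit lies between these, at 1.58–1.60 with 50% non-response.

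Fits to exact expected counts, with 20% comorbid, non-response 20–50%, and comorbid non-responders stopping as often as other non-responders:

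| Non-responders / non-comorbid responders stopping | Comorbid responders stopping | True 2.0 reads | True 1.0 reads | AUC with discontinuation |
|---|---|---|---|---|
| 90% / 30% | 30% | 2.00 | 1.00 | 0.79–0.82 (all 90/30 rows) |
| 90% / 30% | 45% | 1.46–1.60 | 0.72–0.77 | |
| 90% / 30% | 55% | 1.24–1.40 | 0.61–0.66 | |
| 70% / 30% | 45% | 1.67–1.82 | 0.82–0.88 | 0.68–0.73 (link as a whole) |
| 70% / 30% | 55% | 1.53–1.72 | 0.74–0.82 | |
| 60% / 40% | 50% | 1.90–1.95 | 0.94–0.96 | 0.59–0.62 (both 60/40 rows) |
| 60% / 40% | 55% | 1.86–1.92 | 0.92–0.95 | |

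Without discontinuation the AUC is 0.50–0.56. With 5% comorbid instead of 20%, the 90/30 results for a true 2.0 are 1.46–1.60 and 1.23–1.39, so prevalence hardly matters.

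A second set of inputs agrees: 15% comorbid, 48% non-response without comorbidity, and comorbidity doubling the odds of stopping at a given response status. A true 2.0 then reads 1.50 with 20%/60% of responders/non-responders stopping, and 1.37 with 30%/90%.

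**4. Sensitivity and specificity.** Strong link (90/30), true OR 2.0, cut-off 0.5:

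| Non-response | Without discontinuation | With discontinuation |
|---|---|---|
| 50% | 0.25 / 0.85 | 0.90 / 0.66–0.70 |
| 30% | 0 / 1.00 | 0.90 / 0.66–0.70 |
| 20% | 0 / 1.00 | 0–0.27 / 0.92–1.00 |

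**5. Chance of passing the screen.** This uses a noncentral chi-square with 1 df at level 0.1. With non-response rate r, stopping rates p₁ (non-responders) and p₀ (responders), and mean p̄ = r·p₁ + (1 − r)·p₀, the noncentrality is λ = N·r(1 − r)(p₁ − p₀)² ÷ [p̄(1 − p̄)]. For example, N = 400, r = 0.5 and 60% against 40% give λ = 400 × 0.25 × 0.04 ÷ 0.25 = 16 and a 99% chance. For N of 200–400 and r of 20–50%, the chance is about 100% at 90% or 70% against 30%, 74–99% at 60% against 40%, and 31–64% at 50% against 40%.

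**6. Age omitted, no true comorbidity effect.** Take 25% older patients, comorbidity 50% against 10%, and non-response 45% against 25%:

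- comorbid: 0.075 non-responders, 0.125 responders;
- not comorbid: 0.225 non-responders, 0.575 responders;
- crude OR = (0.075 × 0.575) ÷ (0.125 × 0.225) = 1.53.

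With older non-response at 15%, the same sum gives (0.0375 × 0.6125) ÷ (0.1625 × 0.1875) = 0.75. Over the grid (15–25% older, comorbidity 40–50% against 10%), a null comorbidity reads 0.75–1.53 with 25% non-response in younger patients and 0.68–1.47 with 50%. Adjusting for age returns 1.00 in every cell.

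**The case against.** Discontinuation is only a screened candidate, and the damage depends on rates that the documents do not give. Protocol 6.1 can be read as closing the reference period at lack of response, so late stops would arise mainly among 10-week responders. Starts were in 2011–2013, which leaves responders years in which to stop. That raises their stopping rate and moves the primary non-response model towards the weak link, where the bias is small. This stands as a limit on size. It does not give the variable a place in the model, and even the weak link passes the screen in 74–99% of cases.

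The table also holds comorbid non-responders at the same stopping rate as other non-responders. In the 90/30 case (comorbid responders 45%, 50% non-response overall), a true 2.0 reads 2.01, 1.79, 1.58 or 1.38 if comorbid non-responders stop in 80%, 85%, 90% or 95%. The range is therefore wider than the table shows. The unbiased value, however, needs comorbidity to make non-responders stop less often and responders more often.

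Three further points stand. AUC is not a planned output, and at 20% non-response the planned pair can stay at 0/1.00. The 0.25/0.85 baseline is fragile: if non-comorbid risk is exactly 50%, it becomes 0.25/0.86 or 1.00/0.00 depending on how ties are classified. The effect on the loss-of-response model is not quantified, because the documents give no rate for it.

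On age, the general wording about sociodemographic covariates could be meant to include it, and the omission may be a drafting slip. But the screen runs on the explicit list, and working status, through its retired category, is only a coarse proxy. Whether age confounds here, and in which direction, cannot be shown from the documents.

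**Conclusion.** The point holds and should be fixed before analysis. A variable that is partly a consequence of the outcome, and can post-date it, is eligible for both primary models under a rule that favours its selection. No other part of either document corrects this.

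If it is retained, discrimination is overstated. The comorbidity odds ratio is unchanged when comorbidity affects stopping only through response. With a separate route, a true 2.0 reads between 1.24 and 1.95 across the tabulated cases, and a true 1.0 reads between 0.61 and 0.96, a spurious protective association. These sizes rest on the assumed stopping rates and apply to the primary non-response model. For loss of response, the argument rests on the order of events alone.

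The absence of age is a lesser but real gap: the stated sociodemographic adjustment is not delivered, with an effect of unknown direction.

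**What to change.** 1. Delete discontinuation of the biologic from the SAP 7.2 candidate list for both models. Keep it as a descriptive result in SAP 6.1.
2. Add age at start of the biologic, as a continuous covariate, to both models. It can be derived from recorded age, the consent date (already used in SAP 5.3) and the starting date of the biologic. Forcing it in, rather than screening it at p below 0.1, is recommended; the essential step is that it enters the plan. It counts towards the variable limit in Protocol 7.1 and 7.4.
3. Optional: a pre-specified sensitivity analysis adding baseline activity (HBI for CD, PMS for UC), with a stated rule for missing scores. It stays out of the main model because severity may lie on the path from comorbidity to response (SAP 7.3 models severity on comorbidity) and because SAP 7.1 allows for unavailable indexes. No size is claimed for it.

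The cost is SAP wording only, with no new data. The screened list falls from 29 to 28, age uses 1 df and one place in each model, and the sample stays at 200 per disease.
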